Tobacco Programs. US Clinical Practice Guidelines⁵ recommend tailoring smoking cessation interventions to readiness to quit smoking, combining counseling and pharmacotherapy, and using strategies including Motivational Interviewing for those not ready and cognitive and behavioral counseling strategies for those who are ready to quit. However the guidelines note the relative lack of effective interventions targeting the young adult population. Compared to other age groups, young adults are less likely to use behavioral or pharmacotherapy interventions for smoking cessation,⁴⁶ and report little intention to use common approaches to smoking cessation.⁴⁷ Studies of tobacco treatment have reported great challenges in recruiting young adults.^{48, 49} Online smoking cessation strategies (e.g., websites designed to help people quit smoking) reach large samples of smokers⁵⁰ but tend not to have a personalized approach to smoking cessation or to have follow-up treatment contacts.⁵¹ Young adults are less likely to take advantage of these cessation resources, and studies of web-based smoking cessation programs have been associated with large drop-offs in engagement of smokers throughout the course of participation.⁵²⁻⁵⁵ Websites directly targeted to young adults have promise with respect to feasibility and short-term outcomes, but have typically focused on college students^{56, 57} who are less likely to smoke than less well-educated young adults.^{58, 59} For example, a study ($N = 35$) evaluating Kick It!, a web-based intervention including graphics, quizzes, and other features, provided initial support for its acceptability and feasibility with college students.⁶⁰ Although the 6-month follow-up quit rate of 25.7% was nearly equal to the self-quit rate of 24.8%, 94.1% reported they would consider future participation in web-based programs, supporting the feasibility of this modality of intervention. Obermayer, Riley, Asif, and Jean-Mary⁶¹ developed a smoking cessation program combining web assessment with

individually tailored smoking cessation messages delivered via text messaging to a participant's cell phone. Among those who completed the study ($n = 29$), the 6-week quit rate was 28%, and there was a significant reduction in cigarettes smoked per week among those who did not quit. Thus, there is limited efficacy for tobacco interventions targeting young adults and those that exist mostly target college populations.

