Tobacco Status Project (TSP). The TSP is a smoking cessation intervention implemented entirely through “secret” (Facebook’s word for entirely private) Facebook groups. The intervention has two main features. First, evidence-based strategies have been used to design Facebook posts to be delivered each day for 90 days to intervention groups on Facebook. Posts are based on the US Clinical Practice Guidelines for smoking cessation⁵ and the Transtheoretical Model (TTM) of behavior change,¹²⁹ both recommending treatment be tailored to participants’ readiness to quit. Interventions based on TTM principles have demonstrated efficacy for quitting smoking in adults,¹³⁰⁻¹³⁴ and adolescents.¹³⁵⁻¹³⁸ Further, tailoring treatments is the most promising method available for smokers not immediately ready to quit, as demonstrated by mixed-methods formative work with young adult smokers led by [name].⁴ For those not ready to quit in the next month, posts are based on Motivational Interviewing (MI), a directive patient-centered counseling intervention recommended by the Clinical Practice Guidelines.^{5, 139} There is evidence that MI is effective in increasing future quit attempts among smokers unmotivated to quit including young adults¹⁴⁰⁻¹⁴⁵ and has shown initial efficacy when delivered in an online format to adolescents.^{146, 147} Posts elicit clients’ motivation and importance of changing tobacco use, problems associated with use, and using open-ended questions to elicit “change talk” (a client’s mention of desire, ability, reason, or commitment to change) through using the 5-R’s: relevance, risks, rewards, roadblocks, and repetition, shown to increase likelihood of tobacco quit attempts.^{140, 148} For those ready to quit in the next month, posts incorporate skills from cognitive behavioral therapy, found effective for long-term smoking cessation,¹⁴⁹ as well as the TTM processes of self-liberation (e.g., making a commitment to quit), stimulus control (e.g., removing smoking paraphernalia from the home), and counter conditioning (e.g., engaging in alternative behaviors). Posts also encourage setting a quit date and making a detailed quit plan. Facebook posts include a combination of images, videos, text and polls designed to reflect the experience of young adults and all elicit a response from participants. Posts may suggest that participants use their FB or real social networks for support with alcohol or tobacco reduction. However, they are not required to share any information about substance use on social media. **See Appendix for sample posts.**

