Tobacco Status Project + Alcohol (TSP+ALC). The TSP+ALC intervention design will be informed by results of focus groups (see Section C.4), and the existing TSP intervention. Content targeting heavy drinking will be based on the NIAAA Guides Rethinking Drinking⁹ and Guide to Alcohol Screening and Brief Intervention for Youth,⁸ recommending use of the 5A's to address alcohol use. Early posts are expected to elicit assessment of alcohol use and give links to normative feedback and risks based on use. Recognizing that ambivalence is part of many young adults' experience with changing substance use behavior, early posts will also incorporate MI¹³⁹ strategies, also effective with heavy drinkers unmotivated to quit, including young adults.^{65, 150-152} Strategies used in later posts will focus on combining MI with CBT coping skills to empower participants to prepare for reduction or cessation of alcohol use, setting a specific goal, and making a plan for achieving that goal. Skills will be based on "Tips" from the NIAAA Guidelines for youth and adults.^{8, 9, 153} Core CBT skills will include coping with life problems, understanding alcohol use patterns among young adults, coping with cravings and urges to drink heavily, managing thoughts about alcohol use, problem-solving, refusal skills, and elective skills topics including planning for emergencies, recognizing seemingly irrelevant decisions, managing negative moods and demonstrating assertiveness. **The number of posts each day, and strategies to combine alcohol and tobacco content in posts will be informed by focus groups.**

TSP+ALC will also include weekly "The [name] In" sessions. Strategies used in the sessions, as in TSP, will be based primarily on Motivational Interviewing and cognitive behavioral coping skills to change both tobacco use and HED. Stimulus material for these sessions will be designed before the intervention is launched and will address use of both substances. Content is expected to differ based on the two types of groups (Ready/Not Ready to quit tobacco), and alcohol content will be similar among tobacco readiness groups. Some content will address the relationship among tobacco and alcohol use (e.g., "What do you guys think is the relationship between smoking and drinking alcohol?"), while other content will address either one substance or the other.

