Sample size and power analysis. The sample N of 160 was set primarily for practical and clinical reasons and not driven by estimated effect sizes or hypothesis testing. We expect to have representation (although not equal) among males and females, and across ethnic groups consistent with our current trial of TSP. We also expect to have representation across levels of smoking and drinking, and readiness to quit using both substances. We anticipate an attrition rate of 30% at 3, 6, and 12 months, yielding a final sample size of 112 (56 in each group), enabling us to compare groups on primary and secondary outcomes at each timepoint. This will also generate an effect size estimate that will be useful for powering a larger trial.

A goal of 6 participants will be recruited per week during the 6-month recruitment period, which is in line with recruitment for our feasibility trial and current RCT.¹¹¹

Procedures. Participants will be recruited through Facebook and Craigslist advertisements, using a similar strategy to that of focus group and usability-testing. All advertisements will provide a link to the study’s website, with eligibility questions. If respondents are eligible, then they will be taken to the informed consent webpage. Participants consenting to participate in the study will be asked to verify age by sending proof through email or social media, a process used successfully in [name] previous research. Verified participants will be emailed a baseline assessment. Those completing the baseline assessment will be randomized to either TSP, or TSP+ALC, stratified based on readiness to quit smoking (Ready in the next 30 days, Not Ready in 30 days) and smoking pattern (daily vs. non-daily), variables known to be related to outcomes and addressed by the intervention.¹⁶¹ A stratified random assignment program will be developed in consultation with [name], and used currently in [name] RCT of TSP. All participants will then be assigned to a secret group tailored to their condition and readiness to quit tobacco. Groups will begin when there are approximately 12 participants enrolled, as that has been deemed the optimal number based on analyses of engagement in our previous work.^{109, 162} Groups will receive one social media post daily for 90 days and weekly “The [name] In” counseling sessions managed

[figure not shown]

Figure 2. Participant flow through the study

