Analyses for Specific Aim 3 (Engagement and Patterns of Social Interaction). Analyses will use Facebook data extracted from the private groups we develop on Facebook using the Facebook API. All data will be de-identified and transferred to **[name]**, expert on social media analytics at Drexel University, for analysis. The data will include the content of the posts and comments, the activity of each participant (e.g., number, content, and time of all comments), and interactions among participants. We will determine patterns of engagement, type of posts that are most “engaging” to participants, and relate engagement to smoking and drinking outcomes using three main analyses: **(1) Patterns of engagement:** Total number of “likes” and comments to Facebook groups over the 3 month intervention period will be tallied for each group (TSP, TSP+ALC), and the non-parametric Kruskal-Wallis ANOVA will compare likes and comments in each intervention and include covariates of baseline characteristics (readiness to quit tobacco/alcohol, daily/non-daily smoking status, gender) and group membership; a social network analysis will examine the interaction patterns among different types of users with which participants engage in each intervention; a content analysis will evaluate the content of comments within each group and observe differences among the two groups; **(2) Success of specific posts:** To evaluate which posts are most successful at engaging participants, Drs. [name] and [name] will collaborate on coding posts based on content type (e.g., alcohol/tobacco, Motivational Interviewing, specific CBT skills). Specific codes will be determined upon design of the TSP+ALC intervention). ANOVA will then be used to examine likes and comments by post type within each group (TSP, TSP+ALC) **(3) Engagement and outcomes:** We will compare TSP and TSP+ALC groups on the relationship between intervention engagement (FB comments) and primary tobacco and alcohol outcomes (abstinence, heavy drinking days) at the end of the 3 month intervention period. Logistic regression will be used to analyze tobacco abstinence, and linear regression for days of heavy drinking at 3 months, controlling for any baseline differences in treatment groups. Kruskal-Wallis tests will evaluate the effect of incentive condition (personal, altruistic, no incentive) on comments to the Facebook group, in both the full sample and only those who made at least one comment to the group to address likely skewed data.

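### Aim 3 post-success ANOVA: for tobacco posts, an MI-versus-CBT comparison within an arm is largely a comparison of Not Ready with Ready Facebook groups

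*Combined protocol and SAP*

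**What the plan says.** Section C.9, Analyses for Specific Aim 3, item (2), sets out to find which posts engage participants best. It describes "coding posts based on content type (e.g., alcohol/tobacco, Motivational Interviewing, specific CBT skills" and adds that "Specific codes will be determined upon design of the TSP+ALC intervention". It then states: "ANOVA will then be used to examine likes and comments by post type within each group (TSP, TSP+ALC". The word group in that sentence means trial arm, so Ready and Not Ready audiences are pooled. No term is named for readiness, Facebook group, group size or programme day. Item (1) of the same section does list readiness and group membership as covariates.

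Section C.5 (TSP) allocates tobacco content by readiness: "For those not ready to quit in the next month, posts are based on Motivational Interviewing (MI", whereas "For those ready to quit in the next month, posts incorporate skills from cognitive behavioral therapy". Section C.8 (Procedures) forms the audiences the same way: "All participants will then be assigned to a secret group tailored to their condition and readiness to quit tobacco".

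For TSP+ALC, C.5 does not divide alcohol posts by readiness, and says that alcohol content of the weekly sessions will be similar in both kinds of group. It does order alcohol posts in time: early posts bring in assessment, feedback and MI, and "Strategies used in later posts will focus on combining MI with CBT coping skills".

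**The concern.** If MI-coded and CBT-coded tobacco posts reach different people, a difference in likes or comments between them may come from the people and not the posts. The ANOVA as worded has no way to tell these apart and would report the difference as an effect of post type.

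A second problem compounds this. Each Facebook group receives about 90 posts, and a talkative group raises the counts on all of them. A plain ANOVA treats those posts as independent, so for a contrast that runs between Facebook groups it works as if it had hundreds of observations when it has a handful of groups.

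At stake is the item's stated purpose, ranking content by engagement, and the Aim 3 paper on Facebook data listed in the C.12 timeline. No primary or secondary outcome is affected.

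**Working it through.** The plan gives no sample size, power or error rate for this ANOVA, so there is no figure of its own to reproduce. One consistency check: 16 groups × 10 members = 160, which matches the planned N.

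**Inputs from the documents**
- 8 Facebook groups per arm, 4 Ready and 4 Not Ready, about 10 members each (C.5, paragraph on the weekly sessions).
- One post a day for 90 days (C.8, Procedures).
- Tobacco posts: MI-based for Not Ready, CBT skills for Ready (C.5).
- 19% ready to quit within 30 days in the team's ongoing TSP trial (preliminary work).

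**Step 1. Can readiness be adjusted for in TSP?** Take the allocation as exclusive, with design columns (intercept, CBT, Ready). Every MI post in a Not Ready group has row (1, 0, 0), and every CBT post in a Ready group has row (1, 1, 1). The CBT and Ready columns are identical, so the rank is 2 of 3. Adding readiness as a covariate does not make the content effect estimable.

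**Step 2. TSP+ALC.** Assumptions: alcohol posts are 25%, 50% or 75% of the total; they switch from MI to MI+CBT at day 45 in both readiness strata; MI+CBT counts as CBT.

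| Alcohol share | Correlation of CBT with Ready | Correlation of CBT with days after 45 |
|---|---|---|
| 25% | 0.76 | 0.24 |
| 50% | 0.50 | 0.50 |
| 75% | 0.26 | 0.74 |

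With additive terms for readiness, substance and late day the model has full rank (5 of 5). Allowing readiness and day effects to differ by substance gives rank 6 of 7. The overlap with readiness is thus partial, and separating content from readiness and day depends on assuming additivity.

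**Step 3. Consequence for the test in TSP.** One-way ANOVA on Poisson counts, one record per post per Facebook group, 90 posts per group, exclusive allocation, no true content effect, assumed mean of 2 comments per post, 1,000 runs. Share of runs with p < 0.05:

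| Scenario | 4 Ready, 4 Not Ready | 2 Ready, 6 Not Ready |
|---|---|---|
| No readiness effect, no group variation | 5% | 6% |
| Ready comment 1.25 times as much, no group variation | 99% | 98% |
| Ready comment 1.5 times as much, no group variation | 100% | 100% |
| No readiness effect, group log-SD 0.2 | 48% | 51% |
| No readiness effect, group log-SD 0.4 | 72% | 72% |

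The last two rows show clustering alone. They apply to MI versus CBT because that contrast runs between Facebook groups; they do not carry over to contrasts in which every group receives both types.

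The 2/6 split is included because, if the 19% carried over, 0.19 × 160 / 2 = 15.2 participants per arm would be Ready. That is 15.2 / 12 = 1.3 to 15.2 / 10 = 1.5 groups.

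**Step 4. Size of apparent effect, as illustration.** If Ready members comment 1.25 or 1.5 times as often, CBT posts appear 25% or 50% better with equal content. If commenting declines exponentially over 90 days, posts in the first half score (1/r)^0.5 times those in the second half, where r is the fraction remaining at day 90. This gives 1.41 for r = 0.5, 1.15 for r = 0.75 and 1 for no decline. The decline matters only where content is ordered in time, which the documents show for TSP+ALC alcohol posts alone.

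**The case against.** The strongest reply is that the plan never commits to MI versus CBT. The codes are examples, to be settled later. Alcohol versus tobacco is the example listed first and is not allocated by readiness; one CBT skill against another within Ready groups is also free of the problem. The wording of C.5 does not strictly exclude MI content from Ready groups. All of this stands and sets the scope. A reader might infer that every post-type comparison is confounded with readiness, or that programme day is an issue in both arms. The documents support neither: they give no day order for tobacco posts.

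A reader might also infer from the 19% Ready share that an MI post is seen by 81/19 = 4.3 times as many members as a CBT post. That does not hold on the plan's own numbers. C.5 plans 4 Ready and 4 Not Ready groups of about 10 per arm, so the audiences are 40 and 40, a ratio of 1. The 19% comes from a trial for which the documents report no heavy-drinking entry criterion, and the ratio would also require counts summed across groups.

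The evidence that engagement differs by readiness or falls with time is indirect. The QuitNet comparison is of maintenance with early action, not Ready with Not Ready. The Background statement that "studies of web-based smoking cessation programs have been associated with large drop-offs in engagement of smokers throughout the course of participation" concerns websites. The team's Facebook feasibility trial reports 92% participation over the full three months, and this study rewards commenting. The size and even the sign of any bias are therefore unknown. The non-separability in Step 1 does not depend on them.

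Finally, nothing says this item will decide a redesign, and the next step named in C.13 is a powered trial. This limits the severity but does not rescue the interpretation.

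**Conclusion.** The point holds for MI-coded against CBT-coded tobacco posts within an arm: that contrast is largely Not Ready against Ready. With exclusive allocation the two cannot be separated by covariate adjustment. The plain ANOVA also ignores clustering by Facebook group. In TSP+ALC the aliasing with readiness is partial, and for alcohol posts MI versus MI+CBT is also tied to programme day.

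The rank result follows from the allocation described in C.5 and C.8, taken as exclusive. The rejection rates rest further on an assumed mean count, assumed readiness ratios and assumed group variation, and on one record per post per Facebook group, a unit the plan does not state. The 1.5-fold and 1.41-fold figures are illustrations only.

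Severity is minor: one exploratory Aim 3 sub-analysis in a pilot.

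**What to change.** Reword item (2) of the Aim 3 analyses:

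- Compare post types only among posts delivered to the same readiness stratum within an arm.
- Use one record per post per Facebook group, and model the like and comment counts with a count model that includes Facebook group, programme day and an offset for the logarithm of group size. Enter Facebook group as a fixed effect where a stratum has only a few groups, which is likely for Ready if the 19% share recurs.
- Do not report MI versus CBT across readiness groups as a content effect. State that the design cannot separate it from readiness, and that adding readiness as a covariate does not cure this.
- For TSP+ALC alcohol posts, note that MI versus MI+CBT depends on how programme day is modelled.

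The cost is analysis wording only. Readiness is a randomisation stratum, Facebook group is known by assignment, and the extracted data include the time of each comment. The change is best made when the codes are finalised.

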While preliminary work is not necessary for a Planning Grant application (R34), our team has pilot data and expertise that is directly relevant to this application.

Development, feasibility and efficacy of the Tobacco Status Project (TSP). During her postdoctoral fellowship, [name] led a mixed-methods study to determine how young adult smokers would like to use Facebook to help change smoking behavior. About a third (31%) of survey respondents reported they would want to quit smoking using Facebook, and interest was greater among those more motivated to quit, who had made a quit attempt in the past year, and had previously used the Internet for assistance with a quit attempt (all $p<0.01$). In qualitative interviews, social support and convenience were identified as strengths of a Facebook intervention, while privacy was the main concern.⁴

[name] is currently funded with a five-year K23 career development award from NIDA to develop and test the feasibility and efficacy of Tobacco Status Project, combining Facebook contacts tailored to participants' readiness to quit smoking with a 12-week cessation program consisting of 7 state-of-the-art group cognitive-behavioral sessions occurring over Facebook text chat. A feasibility trial enrolled 79 young adults who formed 7 Facebook groups. Follow-up rates were 84% and 72% at 6 and 12 months, respectively, and reported 7-day abstinence was 21% at 6 months (9% biochemically-verified) and 18% at 12 months (9% verified).^{6,7} From baseline to 12-months, there was a significant increase in the proportion prepared to quit (13% to 46%, $p<.001$), 35% reduced their cigarette consumption by 50% or greater, and 67% reported a 24-hr quit attempt. Engagement in the intervention was high, with 92% participation in the full 3 month intervention and 61% commented on at least one post, with more commenting among those randomized to receive a personal monetary incentive.¹⁰⁹ Participants reported reading most of the Facebook posts (mean usability rating=3.3/4) and interactions from counseling sessions (3/4), thinking about what they read (3/4) and would recommend the program to others (3.3/4). Given low participation in CBT sessions (7 of 79 participated) but extremely high engagement (6/7 sessions attended on average) we incorporated the sessions directly into the Facebook groups for a larger efficacy trial currently underway.

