In a 3-year controlled trial, we are randomizing 480 young adult participants to either TSP or referral to the National Cancer Institute Smokefree.gov website (control). In 34 weeks, we have randomized 309 young adult smokers, consistent with the proposed timeline, 19% were ready to quit smoking in the next 30 days, and the TSP group has 19 groups actively running or completed. Among TSP participants in groups that have completed the 3-month intervention (n=66), 73% commented at least once to their Facebook group. At 3 month follow-up (treatment end), follow-up rate is 71%, biochemically-verified 7-day point prevalence abstinence among completed cases is 7.1% in the TSP group and 0% in the control group. A majority of participants in both groups reported a 24 hour quit attempt during the 3-month intervention period (62% TSP; 60% control). More participants in the TSP group reported intention to quit smoking in the next 30 days (43%) than those in the control group (35%). At baseline 68% of the sample drank alcohol in the past month and 51% of all drinkers reported current HED. Although promising, there is a need to determine whether expanding the intervention to address multiple substance use will yield maximal effectiveness. **This pilot work will directly inform the present study.**

Facebook Recruitment. Drs. [name] and [name]'s research has previously found social media to be an efficient and affordable source of recruitment for young adult smokers. A survey study (N=1987) reported a cost of \$4.28 per valid completed online survey, far more affordable and targeted than other online recruitment methods.¹¹⁰ The TSP feasibility trial, discussed above, reported a cost of \$8.80 per eligible consented young adult smoker into our Facebook intervention.¹¹¹ Gender and ethnicity have differed by online recruitment source in our work (e.g., Craigslist, Facebook, survey sampling), suggesting the utility of combining recruitment methods.¹¹² **Our experience with social media recruitment will inform recruitment in the present study.**

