through the study's private group pages. If participants wish to have private study interactions with study staff they can do so at any time. Three-month follow-up assessments will be emailed to participants upon completion of treatment.

Informed consent, baseline and 3, 6, and 12 month assessments will be delivered using the online survey program Qualtrics, which is HIPAA-compliant, has been used often in medical research, and is being used successfully by [name] for her current Facebook intervention study. Verification of non-smoking status will be conducted for all participants reporting no smoking in the past 7 days at the post-test assessment using mailed saliva cotinine test kits and verified online as described in the **Measures** section. Participants will receive their choice of Amazon or Best Buy gift cards in the amount of \$20 for each 20-30 minute online survey, and a bonus \$20 for completing all assessments, for a total of \$100 possible compensation for participation. Amazon and Best Buy were chosen as retail outlets given their overwhelming popularity among a large choice of retailers given in [name] previous studies with young adult smokers.^{4, 111} Assessments will not be considered complete until staff receives verification of abstinence.

Measures.

Primary outcome (tobacco):

- **Biochemically-verified 7-day point prevalence abstinence from all tobacco products** will be assessed at 3, 6, and 12 months. Participants reporting no smoking in the past 7 days will be coded as abstinent from cigarettes. Those reporting 7-day abstinence will be mailed a saliva cotinine test kit, and record two pictures: one giving a saliva sample, and another of the test result. Participants with a salivary cotinine level <11 ng/ml, indicating nonsmoking,¹⁶³ will be considered confirmed nonsmokers. Biochemical verification is recommended in randomized trials with sample sizes under 500,¹⁶⁴ saliva cotinine test kits have been successfully mailed to participants in previous studies,¹⁶⁵ and [name] is using this method successfully in her K23 Facebook smoking cessation RCT with young adults (to date, 50% reporting 7-day abstinence have successfully completed biochemical verification). If participants indicate use of an electronic nicotine delivery-system to aid in smoking cessation, saliva cotinine and reported ENDS use will be recorded and reported separately from biochemically verified abstinence.

Secondary outcomes (tobacco):

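### Aim 3 compares the arms' engagement–abstinence slopes by logistic regression with about 4 verified quitters expected per arm and names no sparse-event method; a Firth-penalised fit is a near-costless improvement

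*Combined protocol and SAP*

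**What the plan says.** C.9, Analyses for Specific Aim 3, part (3) Engagement and outcomes, sets the comparison: "We will compare TSP and TSP+ALC groups on the relationship between intervention engagement (FB comments) and primary tobacco and alcohol outcomes". The time point is the end of the 3-month intervention, and the method is: "Logistic regression will be used to analyze tobacco abstinence, and linear regression for days of heavy drinking at 3 months". The model also adjusts for any baseline differences between the arms, without fixing their number. No penalised or exact method, minimum event count or fallback is given.

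C.3 and the Measures part of C.8 define the primary tobacco outcome as biochemically verified 7-day abstinence. C.8 (Sample size and power analysis) says: "The sample N of 160 was set primarily for practical and clinical reasons and not driven by estimated effect sizes or hypothesis testing". It continues: "We anticipate an attrition rate of 30% at 3, 6, and 12 months", "yielding a final sample size of 112 (56 in each group".

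For the likely event rate, the preliminary-work section before C.3 reports month-3 results from the team's ongoing TSP trial: "biochemically-verified 7-day point prevalence abstinence among completed cases is 7.1% in the TSP group and 0% in the control group". For the earlier feasibility trial it says: "reported 7-day abstinence was 21% at 6 months (9% biochemically-verified".

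**The concern.** Comparing a relationship between arms means estimating an arm-by-engagement interaction. With a binary outcome, the precision of each arm's slope depends mainly on the number of quitters in that arm, not on the number of participants. If an arm has no quitters, or if its quitters all lie at one end of the comment range, maximum likelihood has no finite slope for that arm. Short of that, its estimates with few events tend to lie too far from zero and vary widely.

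C.8 says the pilot should yield an effect-size estimate for a larger trial, so the quality of estimates matters even where no test is planned. If the planned fit fails and no alternative has been written down, a rescue method would be chosen after the data are seen.

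**Working it through.** **The plan's own figure.** 160 × (1 − 0.30) = 112, or 80 × 0.70 = 56 per arm. This reproduces the stated sample. The plan gives no power, alpha or effect size, so there is no power figure to reproduce.

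**Expected events at month 3.**
- Verified quitters per arm: 56 × 0.071 = 3.98 (central 95% binomial range 1 to 8). This applies the TSP rate to both arms; no TSP+ALC rate is given.
- Both arms: about 8 events. The model needs at least 4 parameters (intercept, arm, engagement, interaction), so 8 / 4 = 2 events per parameter before any covariate.
- P(2 or fewer quitters in a given arm) = 23%.
- P(no quitters in a given arm) = 0.929^56 = 0.016, so P(none in at least one arm) = 1 − (1 − 0.016)² = 3.2%.

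**Sensitivity of the count per arm.**
- 9% verified (feasibility trial, 6 months): 56 × 0.09 = 5.0.
- All 80 imputed at 7.1%: 80 × 0.071 = 5.7.
- Self-report at 7.1% / 0.50 = 14.2%: 56 × 0.142 = 8.0. The 0.50 comes from C.8: "to date, 50% reporting 7-day abstinence have successfully completed biochemical verification". This assumes that every completed test confirmed abstinence.
- 21% self-reported: 56 × 0.21 = 11.8.

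**Simulation set-up.** The documents give only the share who commented at least once (73%, hence 27% zeros). The shape of the comment count and the true slopes are assumptions. Model A: non-zero counts are 1 plus a negative binomial (mean 15, size 0.7), entered as standardised log(1 + count), with a slope of 0.5 in the reference arm. Model B: negative binomial with mean 12 and size 0.6, entered raw or logged, with slopes of ln 2 or ln 4 per SD. Both have 56 per arm and no covariates.

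**Results at 7.1%.**

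| Quantity | Maximum likelihood | Firth |
|---|---|---|
| No finite estimate, model A | about 4% to 6.5% | essentially none |
| No finite estimate, model B | 6% to 15% | – |
| Mean interaction, truth 0.70, model A | 0.78 to 0.91 across runs | 0.68 to 0.70 |
| Mean interaction, truth 0.69, model B | 0.85 to 1.08 (median 0.76 to 0.82) | 0.61 to 0.71 |
| RMSE, truth 0.70, model A | 1.33 | 0.98 |
| Ratio of odds ratios beyond 3-fold, equal slopes, model A | 25% to 28% | 17% |

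Interaction SD in two model A runs: 1.19 / 0.91 = 1.31 and 1.29 / 0.92 = 1.40, so maximum likelihood is about 30% to 40% more variable. A third run gave 1.14 / 0.78 = 1.46. The RMSE reduction is 1 − 0.98 / 1.33 = 26%.

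**False positives.** With equal true slopes, the maximum-likelihood interaction centred on zero. In one model A run, Wald tests rejected in 2.1% of finite fits and 95% intervals covered the truth in 97.9%. With a true interaction of 0.70, rejection was about 6% under either method.

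**At higher event rates (model A, truth 0.70).** At 9%, about 2% of fits fail and RMSE is 1.14 against 0.87 for Firth. At 14%, 0.2% fail and RMSE is 0.80 against 0.70.

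**The case against.** **The analysis does not mislead.** A reader might infer from 4 quitters per arm that the plan will often announce a between-arm difference that is only noise. The calculations do not support that: rejection is below the nominal 5% when the slopes are equal, and the wide intervals show the imprecision. The 25% to 28% beyond 3-fold counts point estimates without their intervals. This objection stands.

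**The real limit is size, and the plan discloses it.** Firth still puts 17% of equal-slope trials beyond 3-fold, and its SD stays at about 0.8 to 1.2. This also stands: penalisation improves the estimate but does not make it precise.

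**The text says only logistic regression.** Firth's method is a way of fitting that model, so the plan does not exclude it. That is true, but the usual default is maximum likelihood, and nothing tells the analyst to depart from it.

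**The event count may be higher.** C.9 (Preliminary efficacy) plans two outcome sets for smoking tests, only one of them restricted to verified abstinence; the 7.1% is interim; and C.5 offers starter patches. However, the two-set text sits under Aim 2, and Aim 3 refers to the primary outcome, which is verified. At 9% or 14% the failures shrink, yet Firth keeps the lower RMSE. The multiple imputation in C.9 is stated for the primary model and would add no information here.

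**Conclusion.** The point holds as a low-severity improvement to the choice of estimator. At about 4 verified quitters per arm, unpenalised fitting has no finite answer in roughly 4% to 15% of trials. When the slopes truly differ, it overstates the difference by about 0.1 on 0.70, and by up to 0.39 on 0.69 under the least favourable assumptions tried. Its interaction estimate is about 30% to 40% more variable than Firth's.

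Two stronger readings are not supported. Inflation is a tendency when the slopes differ, not a general property: with equal slopes the interaction is centred on zero. Nor do the documents require the between-arm contrast to give way to a pooled engagement slope. That would answer a different question from the one Aim 3 asks, and it is optional.

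The event count rests on the 7.1% TSP rate applying to both arms. The percentages rest on an assumed comment distribution and assumed slopes, so they should be read as ranges.

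**What to change.** In C.9, Aim 3, part (3), keep the planned comparison of the arms. State that the abstinence model, with its arm-by-engagement interaction, will be fitted by Firth-penalised logistic regression with profile penalised-likelihood intervals. State also that the interaction will be reported as an estimate with its interval.

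The cost is a few words in the analysis plan. Standard software fits the model, and recruitment, visits and data collection do not change. The downside is slight shrinkage of estimates toward zero. The write-up should expect an imprecise contrast even so, and should say that the pilot's size is the reason.
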